8.3.2.2 Analysis of Secondary Efficacy Endpoints

8.3.2.2.1 Analysis of Key Secondary Efficacy Endpoints

Relative change from baseline in ppFEV₁ through Week 24

Analysis for the relative change from baseline in ppFEV₁ through Week 24 will be similar to that for the primary analysis. The LS Mean (SE) of the overall treatment difference between TEZ/IVA and placebo in the relative change from baseline in percent predicted FEV₁ from Day 15 through Week 24 will be presented along with the 95% confidence interval and a 2-sided *P* value.

The LS Mean (SE) of within-treatment group relative change from baseline at each post-baseline visit along with the corresponding 95% CI and p-value will be estimated from the same MMRM model. The LS Mean (SE) of the treatment difference between TEZ/IVA and placebo at each post-baseline visit will be provided along with the corresponding 95% CI and p-value. The LS means (with 95% CI) at each post-baseline visit will also be plotted by treatment group. Summary statistics of raw values and absolute change from baseline in ppFEV₁ at each visit will be presented. The cumulative distribution of the average relative change from study baseline in ppFEV₁ through week 24 will be plotted by treatment group.

Number of pulmonary exacerbations through Week 24

A negative binomial generalized linear model will be used to compare the rates of pulmonary exacerbations over the 24-week treatment period for the two treatment groups. The estimated rate ratio and the associated 95% CI and p-value will be provided. In this model, the dependent variable will be the number of pulmonary exacerbations through Week 24, (including both on treatment events and events after treatment discontinuation). Treatment, sex, age group at screening (<18 vs. ≥ 18 years old), and baseline percent predicted FEV₁ will be included as covariates. The log of time spent in the study will be treated as the offset in this model. A log link function will be used in this model. If the model does not converge, the negative binomial regression model will be replaced with a Poisson regression model with the same covariates, offset variable, and link function.

Absolute change in BMI from baseline at Week 24

Analysis of the absolute change from baseline in BMI at Week 24 will be based on an MMRM model similar to that used for the primary analysis, with baseline ppFEV₁ replaced by baseline BMI, and baseline ppFEV₁-by-visit interaction replaced by baseline BMI-by-visit interaction. The treatment difference in terms of BMI at Week 24 will be estimated from this model, along with the 95% CI and the associated p-value.

The LS Mean (SE) of within-treatment group absolute change from baseline in BMI at each of the other post-baseline visits along with the corresponding 95% CI and p-value will be estimated from the same MMRM model. The LS Mean (SE) of the treatment difference between TEZ/IVA and placebo at the other post-baseline visit will be provided along with the corresponding 95% CI and p-value. The LS means (with 95% CI) at each post-baseline visit will also be plotted by treatment group. Summary statistics for the raw values and the absolute change from baseline in BMI at each visit will be presented. The cumulative

distribution of the absolute change from study baseline in BMI at week 24 will be plotted by treatment group.

Absolute change from baseline in CFQ-R respiratory domain through Week 24

Analysis for the absolute change from baseline in CFQ-R respiratory domain (Pooled 'Children Ages 12 and 13' Version and 'Adolescents and Adults' Version) through Week 24 will be similar to that used for the primary analysis, with baseline ppFEV₁ replaced by baseline in CFQ-R respiratory domain, and baseline ppFEV₁-by-visit interaction replaced by CFQ-R respiratory domain baseline-by-visit interaction. The LS Mean (SE) of the overall treatment difference between TEZ/IVA and placebo in CFQ-R respiratory domain from Day 15 through Week 24 will be presented along with the 95% confidence interval and a 2-sided *P* value.

The LS Mean (SE) of within-treatment group absolute change from baseline at each post-baseline visit along with the corresponding 95% CI and p-value will be estimated from the same MMRM model. The LS Mean (SE) of the treatment difference between TEZ/IVA and placebo at each post-baseline visit also will be provided along with the corresponding 95% CI and p-value. The LS means (with 95% CI) at each post-baseline visit also will be plotted by treatment group. Summary statistics for the raw values and the absolute change from baseline in CFQ-R respiratory domain at each visit will be presented. The cumulative distribution of the average relative change from study baseline in CFQ-R respiratory domain through week 24 will be plotted by treatment group.

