10.3 Method of Assigning Subjects to Treatment Groups

Approximately 490 subjects who meet the eligibility criteria will be randomized (1:1) to 1 of 2 treatment arms. Randomization will be stratified by age at the Screening Visit (<18 versus \geq 18 years of age), sex (male versus female), and FEV₁ severity collected during the Screening Period (<70% versus \geq 70% predicted).

An interactive web response system (IWRS) will be used to assign subjects to treatment. Detailed instructions for randomization will be provided separately.

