12.3.3.1 Analysis of Primary Variables

The primary efficacy endpoint is the absolute change from baseline in percent predicted FEV₁ through Week 24. The primary analysis will be based on a mixed model for repeated measures (MMRM) with percent predicted FEV₁ at each time point as the outcome variable. The null hypothesis to be tested is that the mean change from baseline in percent predicted FEV₁ through Week 24 is the same for the 2 treatment arms. A *P* value of 0.05 or less will be interpreted as sufficient evidence to reject the null hypothesis.

The model will include the absolute change from baseline in percent predicted FEV₁ at each visit as the dependent variables; treatment, visit, and treatment-by-visit interaction as fixed effects; and subject as a random effect, with adjustment for sex (male versus female), age group at the Screening Visit (<18 versus ≥18 years old), and percent predicted FEV₁ severity determined during the Screening Period (<70% versus ≥70% predicted).

In the model, visit will be treated as a class variable, assuming an unstructured covariance matrix to model the within-subject variability. This model imposes no assumptions on the correlational structure and is considered robust. Denominator degrees of freedom for the *F*-test for fixed effects will be estimated using the Kenward-Roger approximation.⁴⁴ If there is a convergence problem due to the use of unstructured covariance matrix, a compound symmetry covariance structure will be used to model the within-subject errors. With a mixed-effects model based on restricted maximum likelihood estimation used for the primary

analysis and assuming that, conditional on fixed and random effects, data are missing at random, no imputation of missing data will be performed.

The primary result obtained from the model will be the estimated main treatment effect through Week 24. The estimated main treatment effect, a 95% confidence interval, and a 2-sided *P* value will be provided. Furthermore, the treatment effect at each post-baseline visit, obtained from the model, will also be provided.

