8.3.2.2.3 Analysis of Other Secondary Efficacy Endpoints

Time to first pulmonary exacerbation through Week 24

Analyses for the time to first pulmonary exacerbation through Week 24 will be based on a Cox regression model that will include treatment, sex, age group at screening (<18 vs. ≥18 years old), and baseline ppFEV₁ as covariates. In addition, the Kaplan-Meier (KM) method

will be used to estimate the cumulative exacerbation-free rate; the associated plot will be provided.

Subjects without any protocol-defined pulmonary exacerbation event by or prior to Week 24 will be considered censored at the date of the last visit (up to Week 24).

Note: If in either treatment group fewer than 5 subjects have pulmonary exacerbations, the Cox regression will not be performed and analysis of time-to-first event will be restricted to the Kaplan-Meier estimates.

Absolute change in sweat chloride from baseline through Week 24

Analysis of this variable will be performed using a model analogous to that used for the primary endpoint, with baseline ppFEV₁ replaced by baseline sweat chloride value, and baseline ppFEV₁-by-visit interaction replaced by baseline sweat chloride value-by-visit interaction. The LS Mean (SE) of the overall treatment difference between TEZ/IVA and placebo in absolute change from baseline in sweat chloride from Day 15 through Week 24 will be presented along with the 95% confidence interval and a 2-sided *P* value.

The LS Mean (SE) of within-treatment group absolute change from baseline at each post-baseline visit along with the corresponding 95% CI and p-value will be estimated from the same MMRM model. The LS Mean (SE) of the treatment difference between TEZ/IVA and placebo at each post-baseline visit also will be provided along with the corresponding 95% CI and p-value. The LS means (with 95% CI) at each post-baseline visit also will be plotted by treatment group. Summary statistics for the raw values and the absolute change from baseline in sweat chloride at each visit will be presented.

Absolute change in BMI z-score from baseline at Week 24 for subjects <20 years old at screening

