Analysis for BMI z-score will be based on an MMRM model similar to that used for the analysis of the absolute change from baseline in BMI at Week 24, with baseline BMI replaced by baseline BMI z-score, and baseline BMI-by-visit interaction replaced by baseline BMI z-score-by-visit interaction. The LS Mean (SE) of the treatment difference between TEZ/IVA and placebo in absolute change from baseline in BMI z-score at Week 24 will be presented along with the 95% confidence interval and a 2-sided *P* value.

The LS Mean (SE) of within-treatment group absolute change from baseline at each of the other post-baseline visits along with the corresponding 95% CI and p-value will be estimated from the same MMRM model. The LS Mean (SE) of the treatment difference between TEZ/IVA and placebo at each post-baseline visit also will be provided along with the corresponding 95% CI and p-value. The LS means (with 95% CI) at each post-baseline visit also will be plotted by treatment group. Summary statistics for the raw values and the absolute change from baseline in BMI z-score at each visit will be presented.

Absolute change in body weight from baseline at Week 24

Analysis of body weight will be based on an MMRM model similar to that used for the analysis of the absolute change from baseline in BMI at Week 24 with baseline BMI replaced by baseline body weight, and baseline BMI-by-visit interaction replaced by baseline body

weight-by-visit interaction. The LS Mean (SE) of the treatment difference between TEZ/IVA and placebo in absolute change from baseline in body weight at Week 24 will be presented along with the 95% confidence interval and a 2-sided *P* value.

The LS Mean (SE) of within-treatment group absolute change from baseline at each of the other post-baseline visits along with the corresponding 95% CI and p-value will be estimated from the same MMRM model. The LS Mean (SE) of the treatment difference between TEZ/IVA and placebo at each post-baseline visit also will be provided along with the corresponding 95% CI and p-value. The LS means (with 95% CI) at each post-baseline visit also will be plotted by treatment group. Summary statistics for the raw values and the absolute change from baseline in weight at each visit will be presented.

Absolute change from baseline in percent predicted FEV₁ through Week 24 using on-treatment measurements only

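### Five secondary SAP models (BMI, CFQ-R, sweat chloride, BMI z-score, weight) contain no FEV₁ term although FEV₁ severity is a randomization stratum; retaining one costs almost nothing and gains a little

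*SAP*

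**What the plan says.** **Randomization.** Protocol 10.3 and SAP 6.3 stratify by age group at screening, sex and FEV₁ severity (<70% vs ≥70% predicted); the protocol describes the third factor as "FEV₁ severity collected during the Screening Period".

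**Protocol models.** The primary model (12.3.3.1) adjusts for sex, age group and "percent predicted FEV₁ severity determined during the Screening Period". In 12.3.3.2 the models for BMI, CFQ-R respiratory domain, sweat chloride, BMI z-score and weight follow the primary model and add the endpoint's own baseline. The severity term therefore stays.

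**SAP models.** The primary model (8.3.1.2) carries FEV₁ only as continuous baseline ppFEV₁ and its interaction with visit. For the other endpoints that term is swapped out:
- BMI (8.3.2.2.1): "similar to that used for the primary analysis, with baseline ppFEV₁ replaced by baseline BMI"
- CFQ-R respiratory domain (8.3.2.2.1): "with baseline ppFEV₁ replaced by baseline in CFQ-R respiratory domain"
- Sweat chloride (8.3.2.2.3): "with baseline ppFEV₁ replaced by baseline sweat chloride value"
- BMI z-score (8.3.2.2.3), built on the BMI model: "with baseline BMI replaced by baseline BMI z-score"
- Body weight (8.3.2.2.3), built on the BMI model: "with baseline BMI replaced by baseline body weight"

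The by-visit interaction is swapped in the same way. By contrast, the time-to-first-exacerbation model lists treatment, sex, age group "and baseline ppFEV₁ as covariates". The exacerbation-count model (8.3.2.2.1) and the Week 24 ppFEV₁ ANCOVA (8.3.2.2.3) also keep baseline ppFEV₁.

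**The concern.** In the SAP primary model, baseline ppFEV₁ does two jobs: it is the endpoint's own baseline and it is the only carrier of the FEV₁ stratification factor. Replacing it with another endpoint's baseline keeps the first job and drops the second. Sex and age group survive in all five models; the third stratification factor does not.

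Stratified allocation makes the treatment estimate more precise if the factor is prognostic, but a model that omits the factor does not credit that precision. The reported standard error is then too large, confidence intervals are too wide, and the test rejects less often than it should.

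BMI and CFQ-R are steps 4 and 5 of the fixed sequence in SAP 8.3.2.2.2, and a miss on BMI also blocks CFQ-R. The documents state power only for ppFEV₁ and exacerbations, so no stated margin protects these two tests. Sweat chloride, BMI z-score and weight lie outside the hierarchy.

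**Working it through.** **1. The plan's own figure.** SAP 6.2 gives SD 8, difference 2.5, 220 per arm and two-sided α = 0.05. The noncentrality is 2.5 / (8·√(2/220)) = 3.28, so power = Φ(3.28 − 1.96) = 90.6%, matching the stated 90% or more. For dropout, 220/0.9 gives 245 per arm, 490 in total. Both reproduce. The plan gives no power, SD or effect size for the five endpoints at issue, so the rest uses a reference test with 80% power without an FEV₁ term.

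**2. Assumed inputs (not in the documents).**
- r, the correlation of baseline ppFEV₁ with the endpoint change after own baseline, sex and age group: 0 to 0.3.
- Screening FEV₁: normal, mean 60, SD 15, truncated to the eligibility range 40 to 90. Baseline equals screening plus noise with SD 4. This puts 74% of subjects below 70 and gives a correlation between stratum and baseline of ρ ≈ 0.737 (ρ² ≈ 0.543).

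**3. Formulas.** Set the residual variance without FEV₁ to 1. The model reports variance 1, but the true variance of the estimate is v = 1 − r²b, on the same scale. Here b = ρ² if only the two-level stratum is balanced, and b = 1 if FEV₁ is fully balanced.
- Noncentrality giving 80% power without the term: d = 1.96 + 0.8416·√v
- Power with continuous ppFEV₁: Φ(d/√(1 − r²) − 1.96)
- Power with the stratum: Φ(d/√(1 − r²ρ²) − 1.96)
- Type I error without the term: 2·(1 − Φ(1.96/√v))

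Example, r = 0.3 and b = ρ²: v = 1 − 0.09 × 0.543 = 0.951 and d = 2.781. Power is Φ(2.781/√0.951 − 1.96) = 81.4% with the stratum and Φ(2.781/√0.91 − 1.96) = 83.0% with continuous ppFEV₁.

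**4. Results** (reference 80% without the term).

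| r | Stratum added (b = ρ²) | ppFEV₁ added (b = ρ²) | ppFEV₁ added (b = 1) | Type I error without term (b = ρ²) |
|---|---|---|---|---|
| 0 | 80.0% | 80.0% | 80.0% | 0.050 |
| 0.1 | 80.2% | 80.3% | 80.3% | 0.049 |
| 0.2 | 80.6% | 81.3% | 81.1% | 0.048 |
| 0.3 | 81.4% | 83.0% | 82.5% | 0.044 |

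Under full balance the type I error at r = 0.3 is 0.040. A simulation at r = 0.3 (490 subjects, blocks of 4 within stratum, 20,000 runs) gave power of 79.5% without FEV₁, 80.9% with the stratum and 82.6% with continuous ppFEV₁. Type I error was 0.043, 0.049 and 0.050 respectively.

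**5. Second derivation, by partial R² of the severity stratum.** With k = √(1 − R²) and the noncentrality fixed at 2.80, power without the term is Φ(0.8416/k) and with it Φ(2.80/k − 1.96).

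| R² | SE reduction | Power without → with | Type I error without |
|---|---|---|---|
| 0.01 | 0.5% | 80.1% → 80.4% | 0.049 |
| 0.02 | 1.0% | 80.2% → 80.8% | 0.048 |
| 0.05 | 2.5% | 80.6% → 82.0% | 0.044 |
| 0.10 | 5.1% | 81.3% → 84.0% | 0.039 |

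The two routes agree: r = 0.3 corresponds to R² = 0.09 × 0.543 ≈ 0.05, and both give a gain of 1.4 points. A separate simulation (440 subjects, blocks of 4 in 8 strata, 10,000 trials per setting) gave 80.6% → 81.9% at R² = 0.05 and 81.2% → 84.3% at R² = 0.10. At R² = 0 power and standard error were the same with and without the term.

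**6. Cost of the term.** One extra parameter inflates the standard error by roughly √((n − 5)/(n − 6)) − 1, which is 0.1% at n = 440. If six visit-specific terms were added, the cost would be about 0.7%.

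**The case against.** The case for leaving the models alone has several parts.

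- **The SAP prevails over the protocol** (SAP Section 3). True, and it settles which model runs. It does not supply a reason for the choice.
- **The SAP follows a coherent rule.** Each change-score model uses treatment, sex, age group and the endpoint's own baseline. The exacerbation count and Cox models have no own-baseline score, so ppFEV₁ stands in as a severity covariate. This is a fair reading, and it means the contrast with those models does not prove an oversight. It still leaves one stratification factor unadjusted without comment.
- **The benefit is unproven.** Nothing in the documents shows that FEV₁ predicts these changes given the other covariates, and the assumed range includes zero gain. The 3-point figure is the most favourable corner: r = 0.3, the continuous term, balance on the stratum only. For the stratum itself the gain is at most 1.4 points, and 0.6 or less for r up to 0.2. This stands and limits the size of the point.
- **Redacted text may hold a rationale or an FEV₁-adjusted supportive analysis.** Possible. But the model sentences for these five endpoints are visible, and a supportive analysis would not change the tests at steps 4 and 5.
- **The term is not quite free for BMI z-score.** That analysis uses only subjects under 20, whose number is not given. One extra term costs about 0.5% of the standard error at n = 100 and 0.9% at n = 60. That matches or exceeds the 0.5% reduction expected at R² = 0.01. This stands for that endpoint, which is outside the hierarchy.

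**Conclusion.** The concern holds as an efficiency point. The five SAP models contain no FEV₁ term, categorical or continuous, although FEV₁ severity is a randomization stratum that the protocol models retain. The visible SAP text gives no reason. Validity is not affected: the estimate is unbiased and type I error is at or below 0.05.

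The size is small and conditional. At an 80% reference power the gain is 0 to 1.4 points from the stratum and 0 to about 3 points from continuous baseline ppFEV₁. These figures rest on the assumed r of 0 to 0.3, the assumed FEV₁ distribution and the assumed reference power. The reading of the text is certain; the benefit is not. The change is worth making because it adjusts for a factor already used in the randomization, at negligible cost in the full-sample analyses, and because it matters most for the two endpoints at the end of the hierarchy.

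**What to change.** Before unblinding, amend SAP 8.3.2.2.1 (BMI, CFQ-R) and 8.3.2.2.3 (sweat chloride, BMI z-score, body weight). Each model should keep either the screening FEV₁ severity stratum (<70 vs ≥70) or baseline ppFEV₁, in addition to the endpoint's own baseline and its by-visit interaction. A main effect is enough. Choose one form and fix it in advance, since adding the term after unblinding would be post hoc. If the omission is deliberate, say so in the SAP and give the reason.

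The cost is a change of SAP wording and one covariate already in the data set: one model degree of freedom, or a few if it is entered by visit. No new data are needed. The stratum is known for every randomized subject, so using it drops nobody from the analysis.

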8.3.2.2.2 Multiplicity adjustment

A hierarchical testing procedure will be used to control the overall Type I error for the multiple endpoints tested at $\alpha = 0.05$. For a test at any step to be considered statistically significant within the testing hierarchy, the test must be statistically significant at the 0.05 level, and all previous tests (if any) within the hierarchy must also be statistically significant. The testing hierarchy is as follows:

1. Absolute change from baseline in ppFEV₁ through Week 24
2. Relative change from baseline in ppFEV₁ through Week 24
3. Number of pulmonary exacerbations through Week 24
4. Absolute change in BMI from baseline at Week 24
5. Absolute change in CFQ-R respiratory domain score from baseline through Week 24

8.3.2.2.3 Analysis of Other Secondary Efficacy Endpoints

Time to first pulmonary exacerbation through Week 24

Analyses for the time to first pulmonary exacerbation through Week 24 will be based on a Cox regression model that will include treatment, sex, age group at screening (<18 vs. ≥18 years old), and baseline ppFEV₁ as covariates. In addition, the Kaplan-Meier (KM) method

will be used to estimate the cumulative exacerbation-free rate; the associated plot will be provided.

Subjects without any protocol-defined pulmonary exacerbation event by or prior to Week 24 will be considered censored at the date of the last visit (up to Week 24).

Note: If in either treatment group fewer than 5 subjects have pulmonary exacerbations, the Cox regression will not be performed and analysis of time-to-first event will be restricted to the Kaplan-Meier estimates.

Absolute change in sweat chloride from baseline through Week 24

Analysis of this variable will be performed using a model analogous to that used for the primary endpoint, with baseline ppFEV₁ replaced by baseline sweat chloride value, and baseline ppFEV₁-by-visit interaction replaced by baseline sweat chloride value-by-visit interaction. The LS Mean (SE) of the overall treatment difference between TEZ/IVA and placebo in absolute change from baseline in sweat chloride from Day 15 through Week 24 will be presented along with the 95% confidence interval and a 2-sided *P* value.

The LS Mean (SE) of within-treatment group absolute change from baseline at each post-baseline visit along with the corresponding 95% CI and p-value will be estimated from the same MMRM model. The LS Mean (SE) of the treatment difference between TEZ/IVA and placebo at each post-baseline visit also will be provided along with the corresponding 95% CI and p-value. The LS means (with 95% CI) at each post-baseline visit also will be plotted by treatment group. Summary statistics for the raw values and the absolute change from baseline in sweat chloride at each visit will be presented.

Absolute change in BMI z-score from baseline at Week 24 for subjects <20 years old at screening

Analysis for BMI z-score will be based on an MMRM model similar to that used for the analysis of the absolute change from baseline in BMI at Week 24, with baseline BMI replaced by baseline BMI z-score, and baseline BMI-by-visit interaction replaced by baseline BMI z-score-by-visit interaction. The LS Mean (SE) of the treatment difference between TEZ/IVA and placebo in absolute change from baseline in BMI z-score at Week 24 will be presented along with the 95% confidence interval and a 2-sided *P* value.

The LS Mean (SE) of within-treatment group absolute change from baseline at each of the other post-baseline visits along with the corresponding 95% CI and p-value will be estimated from the same MMRM model. The LS Mean (SE) of the treatment difference between TEZ/IVA and placebo at each post-baseline visit also will be provided along with the corresponding 95% CI and p-value. The LS means (with 95% CI) at each post-baseline visit also will be plotted by treatment group. Summary statistics for the raw values and the absolute change from baseline in BMI z-score at each visit will be presented.

Absolute change in body weight from baseline at Week 24

Analysis of body weight will be based on an MMRM model similar to that used for the analysis of the absolute change from baseline in BMI at Week 24 with baseline BMI replaced by baseline body weight, and baseline BMI-by-visit interaction replaced by baseline body

weight-by-visit interaction. The LS Mean (SE) of the treatment difference between TEZ/IVA and placebo in absolute change from baseline in body weight at Week 24 will be presented along with the 95% confidence interval and a 2-sided *P* value.

The LS Mean (SE) of within-treatment group absolute change from baseline at each of the other post-baseline visits along with the corresponding 95% CI and p-value will be estimated from the same MMRM model. The LS Mean (SE) of the treatment difference between TEZ/IVA and placebo at each post-baseline visit also will be provided along with the corresponding 95% CI and p-value. The LS means (with 95% CI) at each post-baseline visit also will be plotted by treatment group. Summary statistics for the raw values and the absolute change from baseline in weight at each visit will be presented.

Absolute change from baseline in percent predicted FEV₁ through Week 24 using on-treatment measurements only

This analysis will be similar to that used for the primary analysis of the primary efficacy endpoint. The key difference is that this MMRM will include only the measurements up to the date of the last dose for subjects in the FAS. This analysis will use assessments taken between the first dose date through 5 days after the last dose of study drug.

Absolute change from baseline in percent predicted FEV₁ at Week 24 using ANCOVA model

For the absolute change from baseline in percent predicted FEV₁ at Week 24, an ANCOVA model, including treatment, sex, age group (<18 vs. ≥18 years old) at screening, and baseline percent predicted FEV₁ will be used to assess the treatment difference in the absolute change from baseline in percent predicted FEV₁ at Week 24. Missing percent predicted FEV₁ data will not be imputed. The LS Mean (SE) of the treatment difference between TEZ/IVA and placebo in absolute change from baseline in percent predicted FEV₁ at Week 24 will be presented along with the associated 95% confidence interval and a 2-sided *P* value.

[REDACTED]

[REDACTED]

